Subjects will also be swabbed for *S. aureus* and MRSA colonization at the anterior nares and oropharynx. Testing will be performed using two methods: direct microbiology cultures and rapid molecular testing. Microbiologic cultures will be performed by culturing swabs from sites taken to identify *S. aureus* and MRSA carriage will be transported to the research microbiology laboratory at LA BioMed at Harbor-UCLA and plated within 24 hours of collection. Swabs will be processed for *S. aureus* using blood agar and CHROMagar plates for rapid identification of *S. aureus* and MRSA. All *S. aureus* and MRSA isolates will be banked for pulse-field typing, determination of SCCmec type, and presence of the PVL locus (*lukF-PV* and *lukS-PV*). Rapid molecular testing will be performed using the GeneXpert MRSA/SA platform, which is currently available at our site.

Upon confirmation of eligibility, the study coordinators will call the pharmacy to randomize the participant and obtain the oral rinse. The randomization assignment list will be generated in advance by pharmacy. Randomization procedures by an assignment list will be prepared by a computer method. To ensure adequate balance of subjects between the CHG and placebo groups, treatment allocation will be assigned using a random number generation with randomization of blocks of four subjects each. The randomization list will be kept by the pharmacy and treatment allocation randomization will not be shared with either the study staff or patients. The research pharmacists will dispense the appropriate oral rinse to the participant and their parent/guardian. Placebo will be created using the inert vehicles components of CHG, as has been done previously.⁸⁹ Participants and their parent/guardian will be given detailed instructions on the use of the oral rinse both verbally and in a handout in either English or Spanish as preferred by the participant and their parent/guardian.

Subjects randomized to oral CHG will be provided verbal and written instruction on use of CHG oral rinse. Subjects will be asked to use CHG oral rinse twice daily for 7 days. Subjects will be educated to rinse their mouth and gargle with CHG oral rinse for 60 seconds twice a day. Subjects will be instructed to use a watch or other timing device (e.g., smartphone) to ensure that at least 60 seconds have elapses. Research staff will demonstrate the technique for all subjects using drinking water. All subjects randomized to the CHG arm will be provided a new soft bristle toothbrush to prevent recontamination of the oropharynx with *S. aureus* from a contaminated toothbrush. Subjects randomized to usual care will not be provided with any of the above. Regardless of treatment allocation, study staff will educate all subjects' parent/guardian, and subject (if of sufficient age) with the clinical significance of the results of their positive test for oropharyngeal

S. aureus colonization. More specifically, they will be educated that currently testing for *S. aureus* oropharyngeal colonization is considered experimental and that if the test is positive, the clinical significance is unclear. They will also be educated that tens of millions, perhaps over 100 million Americans are colonized in the throat with *S. aureus*, and the vast majority do not suffer consequences of having this bacteria reside in the throat. Upon request, subjects will be provided with a written copy of their results as well as a written description of the clinical significance of oropharyngeal colonization that they can share with their provider, if they wish. All subjects, regardless of treatment allocation, will be provided written and verbal information about *S. aureus* and skin infection prevention and recognition of early disease. These materials were developed for previous studies done by our group.¹⁸

Of note, we debated whether the control group not receiving CHG should receive no therapy or a placebo oral rinse. Obviously, placebo controlled trials are of stronger study design compared to non-placebo controlled studies. More specifically, in non-placebo studies, both patients and investigators will know the treatment allocation, which can lead to bias by both subjects and the investigative team. We did have concern that oral rinses/gargling with placebo or an inert substance may affect *S. aureus* colonization. However, a 1970 investigation examined this issue using quantitative techniques. Investigators asked subjects to gargle with saline and took serial quantitative cultures. They found that gargling specimens taken at 5 minute intervals for 25 minutes showed no significant decrease in organisms concentration, with mean organism concentrations at baseline of 7.11, 6.85 at 5 minutes, and 6.92 at 25 minutes.⁹⁰ This suggests that placebo will have no ability to decolonize oropharyngeal *S. aureus* from study participants.

At the baseline visit, study coordinators will also administer a pediatric *S. aureus* risk factor survey similar to surveys used for previous *S. aureus* and MRSA epidemiologic investigations by our group.^{9,17,18,76,80,84,85} Items from this survey have been based on careful reviews of the literature on *S. aureus* risk factors and have incorporated items used previously by the CDC, Health Departments, and other investigations examining MRSA risk.^{80,84} The baseline survey will collect information about demographics, medical history, antibiotic use, and behavioral risk factors for *S. aureus* infection and colonization. Participants and their parent/guardian will be given phone numbers of the study coordinator for questions. Participants and their parent/guardian will be compensated for their time for this and all study visits.

Follow-up visits

Participants will be asked to come to the research clinic 7 days after initiation of oral CHG, i.e., at the end of their treatment (Visit 2). A subsequent visit will occur at 28 days (Visit 3). The purpose of these visits is to ascertain oropharyngeal eradication of *S. aureus* both short term (primary study outcome) and longer term. Based on previous investigations conducted at our center(s), we estimate a 10% attrition rate.^{75,77,78,81,82} At Visit 2, participants will be swabbed the nares and oropharynx for the presence of *S. aureus* and to complete a follow-up survey about any recurrent infections, new medical history, or receipt of antibiotics. At Visit 3, participants will return to the research clinic to complete a follow-up survey. Study staff will also call all subjects remind them of their upcoming study appointments and at days 14 and 21 to address any questions the participant or their parent/guardian may have about the study. Adverse events will be measured at each scheduled and unscheduled (see below) follow-up visits. Adverse events will be measured using the Medical Dictionary for Regulatory Activities Terminology (MedDRA) version 14.0 or later terms.

Unscheduled visits

If participants or their parent/guardian experience potential adverse drug events that occur during the follow up period, subjects or their parent/guardian will be encouraged to contact study staff. If the event may be of clinical concern, the event will be referred to a study physician and the oral rinse discontinued, if applicable. If deemed necessary by the study physician or the subjects' primary physician, participants will be asked to return to the research clinic for evaluation by a study investigator.

Aim 1: Determine the efficacy of oropharyngeal decolonization among children suffering from CA-MRSA and other *S. aureus* skin infections

To determine if oropharyngeal *S. aureus* colonization can be eradicated, we will perform a prospective, double blind randomized controlled clinical trial of 0.12% oral chlorhexidine (CHG) oral rinse versus placebo for children age 5-17 with *S. aureus* oropharyngeal colonization. We hypothesize that 0.12% CHG rinse will

reduce oral *S. aureus* colonization better than placebo treatment. The findings from this Aim will provide “proof of principle” data on the ability of oral antiseptics to eradicate oropharyngeal *S. aureus* colonization in children.

Power and Sample Size

Using an alpha of 0.05 and expected cure rates of 50% and 10% in the CHG and placebo arms respectively, 54 subjects (27 per group) would be needed for 85% power to detect a 40% absolute difference in cure ($p<0.05$) between groups. Correcting for a 10% attrition rate, 60 enrolled subjects would be needed. To identify 60 subjects with oropharyngeal colonization, and assuming 33% of patients who are high risk for *S. aureus* colonization will have oropharyngeal colonization, 240 subjects will need to be screened to obtain 80 patients that are oropharyngeally colonized with *S. aureus*. Of these, 75% (n=60) will have *S. aureus* detected by the GeneXpert rapid test and will undergo randomization.

Data Analyses and Data and Safety Monitoring

The decolonization rate will be calculated as the number of subjects who remain decolonized divided by the number of subjects, and treatment group differences as differences in these rates. The precision of estimated rates and rate differences will be expressed with two-sided confidence intervals calculated as asymptotically normal approximations to binomial or differences in binomial random variables. The level of confidence for these intervals will be 95%. Statistical significance for differences between treatment groups in cure rates will be determined from Fisher’s exact tests. The level of significance for these tests is 0.05. Factors associated with failure of decolonization in the CHG treatment group will also be examined. Based on prior investigations of *S. aureus* colonization from our group and others, these will include demographics (age, gender, race/ethnicity), co-morbidities, measures of hygiene, number of prior skin infections in the prior year, antibiotic use in the prior year, household history of skin infection, adverse effects and tolerability (see Aim 2, below), and treatment adherence. Additionally, we will examine pathogen level predictors of decolonization failure, based on molecular characterization of baseline isolates (see Aim 3). These factors will include baseline colonization with USA300 strain, presence of qac A/B gene, presence of nasal colonization, presence of nasal colonization with a strain identical to the oropharyngeal colonizing strain, and presence of nasal colonization with a strain differing from the oropharyngeal colonizing strain. Associations will be examined using Chi-squared, Fisher Exact test, Wilcoxon rank sum test, or T-test, as appropriate. Small sample size will preclude multivariable analyses of factors independently associated with failure to decolonize. This analysis will be key to identifying factors associated with decolonization failures. Identification of mutable factors associated with decolonization failure will be key towards improving the success of future efforts at oropharyngeal eradication of *S. aureus*. Identification of non-mutable factors will be key towards identifying groups that may need more intense intervention and or education.

Given this investigation is minimal risk, Data and Safety Monitoring (DSM) will be performed by the Investigative Team. DSM will be performed according to standards of The Eunice Kennedy Shriver National Institute of Child Health and Human Development (NICHD) Policy for Data & Safety Monitoring.⁹¹ These will include reviewing monthly summaries of the number of patients enrolled, age, ethnic and gender makeup, Number of patients retained in the study, number of dropout and lost to follow up, adverse events (AEs), and serious adverse events (SAEs) (See Aim 2, below for further details). Subjects that report treatment related adverse events will discontinue the oral rinse and come to the research clinic for an unscheduled visit.

Aim 2: Assess the safety, tolerability, and compliance of oropharyngeal decolonization among children and their caregivers. We will administer a detailed and systematic survey of side effects, tolerability and compliance of the oropharyngeal decolonization regimen to determine the effects, concerns, and usability of this regimen in children for both the child participants and their parents/caregivers. Findings will identify adverse effects and barriers to use to be considered when possibly administering this regimen in the future.

Data Analyses

Adverse events will be coded to a Medical Dictionary for Regulatory Activities Terminology (MedDRA) version 14.0 or later terms. Verbatim description and the MedDRA System Organ Class and Preferred Term for all adverse events will be contained in the subject data listings. A separate listing sorted

by MedDRA System Organ Class and Preferred Term will include all verbatim descriptions associated with the Preferred Terms.

Data for adverse events will be analyzed using the treatment-emergent signs and symptoms philosophy.

Treatment emergent signs and symptoms are defined as adverse events where:

- onset occurs during exposure to study medication or within 7 days after the last dose of study medication, having been absent prior to receiving study medication, or
- onset reoccurs during exposure to study medication or within 7 days after the last dose of study medication, having been present but stopping prior to receiving study medication, or
- worsening in severity occurs during exposure to study medication relative to the pre-treatment state, when the adverse event is continuous.

All reported adverse events (regardless of treatment-emergent or not) will be included in a by-subject adverse event listing. Only treatment-emergent adverse events will be included in summary tables. The number of subjects (incidence) of treatment-emergent adverse events will be presented as well as the frequency of all adverse events reported.

Summary tables of adverse events will include the following:

- Summary of adverse events by severity and relationship
- Summary of related adverse events
- Summary of Serious adverse events
- A listing of any on-study pregnancies

Percentages of subjects who reported adverse events will each be compared separately among each group using Chi-Square or Fisher Exact tests, as appropriate.

Aim 3: Determine the *S. aureus* genetic backgrounds associated with breakthrough oropharyngeal colonization.

Advances in sequencing technologies and the availability of large computing power and bioinformatics have allowed WGS to become the method of choice to characterize emerging phenotypes.⁷² WGS also allows examination of the relationship between presence of the *qac A/B* gene in *S. aureus* at baseline and treatment response. WGS allows detection of this plasmid-based resistance gene for comparative analysis among a subset of *S. aureus* isolates from our population, as described below.

We will molecularly characterize all baseline *S. aureus* isolates and “breakthrough” (failure) isolates using whole genome sequencing (WGS) for identification of breakthrough *S. aureus* isolates. We will compare breakthrough isolates with baseline nasal and oropharyngeal isolates to determine if breakthrough isolates represent either: a) recolonization with the original oropharyngeal isolate, b) recolonization with the baseline nasal isolate, or c) acquisition of a new *S. aureus* strain. Additionally, we will investigate whether *S. aureus* associated with treatment failures have acquired or possess the *qac A/B* gene.

Sample Size

Data Analyses

WGS will be done in the laboratory of [name] (see Letter of Support), using established techniques.^{92,93} [name] lab has ample experience performing WGS on *S. aureus* and other bacterial pathogens.⁹²⁻⁹⁴ [name] lab will also supply analytic support to assist with interpretation of findings.

WGS sequencing will addresses several hypothesis in those subjects randomized to CHG oral rinses, specifically: a) strains that are found in the oropharynx at end of treatment (Day 7) will be identical genetically to those at baseline and not represent acquisition of new *S. aureus* strain; b) recolonizing *S. aureus* strains at Day 28 among subjects successfully eradicated at Day 7 will represent (re)colonization with the original isolate that colonized the nasopharynx from the same individual (if present at baseline) or a new *S. aureus* strain not present at baseline and; c) nasal isolates found at baseline and follow up will be identical to synchronously identified oropharyngeal *S. aureus* isolates.

Based on data in older adults,¹⁹ we estimate that of the 30 subjects randomized to the CHG arm, 50% will be decolonized, leaving 15 subjects who will be *S. aureus* positive at the oropharynx at the end of treatment. Based on data of recolonization after decolonization in which recolonization can occur after the decolonization regimen is completed,¹⁰ we estimate that a 10% increase in colonization will be seen at Day 28, i.e., 18 subjects will be oropharyngeally colonized with *S. aureus* at Day 28. Thus, we anticipate we will have results in 33 pairs of oropharynx isolates (15 between baseline and Day 7, and 18 between baseline and Day 28, for a total of 66 isolates total). Additionally we will conduct whole genome sequencing on baseline nasal *S. aureus* isolates associated with the subsequent oropharynx isolates identified at Day 7 and/or Day 28. Based on previous data suggesting that ~45% of those colonized at the oropharynx will be colonized at the anterior nares,^{18,46,95} we estimate an additional 30 (45% x 66) nasal *S. aureus* isolates from baseline and follow-up will be present synchronously with oropharyngeal isolates.

In total 96 isolates will undergo whole genome analysis to address the hypotheses outlined above. Specifically, we will examine if decolonization failure of the oropharynx is due to any of the following: 1) a new and distinct *S. aureus* strain; 2) an isolate found at the nares at baseline; 3) an isolate found in the oropharynx at baseline; or 4) an identical strain from baseline but that has acquired with new resistance genes to CHG, specifically *qac A/B*. WGS typing of nasopharyngeal *S. aureus* isolates also allows us to determine if “breakthrough” oropharyngeal strains at Day 7 and/or 28 arise from endogenous or exogenous sources. Given that oropharyngeal and nasal isolates taken from the same person at the same time, are not always genetically identical,¹⁸ one cannot assume that baseline strains will be concordant. Finally testing of nasal oropharyngeal and nasal *S. aureus* at baseline and the Day 7 and 28 follow up visits, can assist in determination if resistance genes to CHG, specifically *qac A/B*, emerged after treatment in non-oropharyngeal, specifically nares sites, as it is known that antimicrobial therapy is associated with collateral damage among strains not specifically targeted by that treatment.³⁷ I.e., oral CHG may result in the emergence of *qac A/B* containing *S. aureus* strain in the nares. Analytically, the above analyses will be descriptive thus there are no power calculations for this aim.

Limitations

This investigation is limited as it is a single center study. However, our center serves a ethnically and socioeconomically diverse population and findings from our investigations have been comparable to similar investigations in other populations.^{18,96,97} Our intervention is also singular in decolonization efforts (oropharynx only). However, no investigation has looked at the effect of *S. aureus* eradication on the oropharynx in children, so the addition of other decolonizing agents would prevent us from determining the efficacy of CHG oral rinse. Additionally, our trial is a “proof of principle” study that is required prior to a more comprehensive trial on *S. aureus* decolonization as a means for SSTI prevention. Finally, we are not performing WGS typing on all colonizing *S. aureus* isolates at all study time points, as it is known that *S. aureus* can colonize not only the nares and oropharynx, but the axilla, inguinal fold, perirectal area, vagina, and areas of skin that have lost integrity.^{42,47,98,99} However, the extra cost of testing these sites for possible sources of *S. aureus* that can later recolonize the oropharynx would be extremely expensive. Thus we chose just to perform testing in sites in which *S. aureus* is most commonly found (nares, oropharynx).

Future Directions

Investigation on prevention of recurrent *S. aureus* SSTI have been extremely disappointing, suggesting more comprehensive decolonization regimens need to be developed, especially those that focus on sites of colonization not previously targeted in clinical trials. Our investigation will be the first study to examine the efficacy of CHG to eradicate *S. aureus* from the oropharynx of children. [name] and his team provide ample experience in the area of MRSA infection and colonization, infectious disease expertise, clinical trials, and pediatrics. Besides the aims addressed for this investigation, our team is poised to address future aims related to *S. aureus* decolonization efforts and SSTI recurrences by generating information on the efficacy of CHG. In summary, the results of this investigation will provide the critical foundation for the development of future clinical trials. Data generated from our investigation will further investigative work on prevention of recurrent *S. aureus* SSTIs, which remain an extremely common and vexing clinical problem for clinicians, and more importantly, patients.

Human Subjects/Investigational New Drug (See General Instructions for page limitations/recommendations)

For this investigation, Harbor-UCLA Medical Center pediatric emergency department providers (MD, NPs) will refer patients agreeable to being approached by research coordinators about the study. If patient and their guardian are agreeable, research staff will approach patients and initiate the informed consent process. If the patient and/or their parent or guardian consent and the patient is eligible, the patient will undergo the first part of the study (oropharyngeal screening for *S. aureus*, which will be evaluated using the GeneXpert platform). Study staff will explain the study to the potential subject's parent or guardian. The informed consent process will be conducted by a study team member in their preferred language (English or Spanish). Written informed consent will be sought, obtained, and documented by a research coordinator and the site's PI using a form approved by the institution's IRB. Subject's who are capable will participate in the informed consent process and those 7-12 will be asked to sign an assent form. Subject's older than 12 will co-sign the consent form with their parent/legal guardian. The informed consent process will explicitly state that if the oropharyngeal screening for *S. aureus* is positive, they agree to participate in the clinical trial and that if the oropharyngeal screening for *S. aureus* is negative, they are not eligible for the clinical trial.

All subjects who have consented will have the rapid *S. aureus* test performed with results shared with the subject's parent/guardian, the subject, and the clinician, if approved by the parent/guardian. Study staff will educate and the subject's parent/guardian, and subject (if of sufficient age), the clinical significance of the results, either positive or negative. More specifically, they will be educated that currently testing for *S. aureus* oropharyngeal colonization is considered experimental and that if the test is positive, the clinical significance is unclear. They will also be educated that tens of millions, perhaps over 100 million Americans are colonized in the throat with *S. aureus*, and the vast majority do not suffer consequences of having this bacteria live in the throat. Upon request, subjects will be provided with a written copy of their results as well as a written description of the clinical significance of oropharyngeal colonization that they can share with their provider, if they wish.

Subjects with a positive screening test will undergo 3 study visits total: baseline/enrollment visit (Visit 1), Day 7 (Visit 2), and Day 28 (Visit 3). Consenting subjects will have their anterior nares and oropharynx swabbed at Visits 1, 2, and 3. A survey will be administered at the initial visit and a follow-up survey will be administered at Visits 2, and 3. The survey administered at Visit 1 will collect information about demographics, medical history, and behavioral risk factors for skin and soft tissue infection and colonization. Subjects will be randomized to 0.12% CHG oral rinse or placebo use for 7 days. All subjects will receive educational materials regarding *S. aureus* and skin infections and their prevention. Those randomized to the intervention will receive additional verbal and written information on use of CHG oral rinse. The survey administered at Visit 2 will collect information about the adherence, tolerability, and adverse events during the intervention period. The survey administered at Visit 3 will collect information about (late) adverse events, changes in household dynamics and individual behavior (e.g., hygiene) that may affect results of Visit 3 nasal and oropharyngeal colonization studies.

Patients at Harbor-UCLA Medical Center come from a diverse racial and ethnic background, with approximately 51% Hispanic, 26% Caucasian, 18% African-American, and 6% "other" (largely Asian and to a lesser extent, mixed race). Two hundred and forty patients are anticipated to be enrolled over 18 months to randomize 60 subjects. Subjects constitute a cross-section of pediatric patients either presenting to our health care facilities that had a history of a skin and soft tissue infection, and will thus consist of pediatric patients age 5-17 and both genders.

There are risks to subject confidentiality, which will be mitigated by all PHI information being kept at the individual site with secure locked filing cabinets and/or on a password-protected computer file. This likelihood of subject confidentiality being broken is minimal. Risks to confidentiality will be protected by keeping all study data in a locked office with access restricted to study personnel. All identifiers will be removed and destroyed when data is logged into an Access database. We will protect against psychological risk to the patient by including an educational discussion with the patient including the nature of bacterial colonization, the risks, current treatments, the lack of acceptance of routine treatments, and the ability to attempt treatment in the case of recurrent infections. If a subject suffers psychological harm, they may contact the Principal Investigator and they will discuss further options. Subjects will be told that their information will not be shared with any persons except for study personnel unless the subject provides

permission. Finally, subjects will be told they can choose not to participate in the study or end their participation at any time without any effect on the care they will receive from their treating physicians or at their treating institutions.

Risks associated with study medication is believed to be minimal. Chlorhexidine-gluconate (CHG) oral rinse is an FDA-approved medication for the treatment of gingivitis. The known side effects of oral CHG oral rinse include staining of teeth and other oral surfaces, an increase in calculus formation; and an alteration in taste perception.¹⁰⁰ All of these potential side effects are transient, reversible, or preventable with education and standard oral hygienic practices (e.g., tooth brushing). All subjects will be educated on the proper use of the oral rinse. Subjects will be asked to report any adverse events to study personnel and to stop the use of the oral rinse if any severe side effects develop (swelling, pain, etc.). Staff will also be able to counsel subjects about the risks and benefits of the oral rinse to decolonize the oropharynx. Study personnel will also have cell phones, which subjects can call to ask questions about the study, use of the intervention oral rinse, and report adverse events. Subjects that report serious adverse events or other medical needs will be referred to the Harbor-UCLA Medical Centers' Pediatric Emergency Department.

An Investigational New Drug (IND) application will not be required, as a clinical investigation of a marketed drug is exempt from IND requirements if all of the criteria for an exemption in § 312.2(b) are met:

- The drug product is lawfully marketed in the United States.
- The investigation is not intended to be reported to FDA as a well-controlled study in support of a new indication and there is no intent to use it to support any other significant change in the labeling of the drug.
- In the case of a prescription drug, the investigation is not intended to support a significant change in the advertising for the drug.
- The investigation does not involve a route of administration, dose, patient population, or other factor that significantly increases the risk (or decreases the acceptability of the risk) associated with the use of the drug product (21 CFR 312.2(b)(1)(iii)).
- The investigation is conducted in compliance with the requirements for review by an IRB (21 CFR part 56) and with the requirements for informed consent (21 CFR part 50).
- The investigation is conducted in compliance with the requirements of § 312.7 (i.e., the investigation is not intended to promote or commercialize the drug product).

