We have several secondary hypotheses: a) decolonization of oropharyngeal *S. aureus* colonization with 0.12% CHG will be sustained at 28 days; b) recolonization of the oropharynx will come from isolates that colonize patients nose and not from development of antimicrobial resistance, including the emergence of CHG-resistant *S. aureus* strains that contain the *qac A/B* genes; and c) predictors of failure to decolonize with CHG will include poor treatment adherence, nasal *S. aureus* colonization, and younger age.

If our primary hypothesis is correct, findings will form the foundation for a larger, randomized, prospective, multi-center, placebo-controlled clinical trial comparing skin, nasal, and oropharyngeal decolonization vs. standard of care decolonization regimen for the prevention of recurrent *S. aureus* skin infections. If oral CHG rinse is unable to decolonize the oropharynx, then other more aggressive oropharyngeal *S. aureus* colonization eradication strategies in children will need to be tested.

B. Specific Aim(s) of the Project

1) Determine the efficacy of oropharyngeal decolonization among children with a history of CA-MRSA, CA-*S. aureus* or skin and soft tissue infection (SSTI). To determine if oropharyngeal *S. aureus* colonization can be eradicated, we will perform a randomized, double blind placebo-controlled controlled clinical trial comparing 0.12% oral chlorhexidine (CHG) oral rinse to placebo among children age 5-17 with *S. aureus* oropharyngeal colonization. We hypothesize that 0.12% CHG rinse will reduce oral *S. aureus* colonization better than placebo treatment. Our findings will provide “proof of principle” data on the ability of oral antiseptics to eradicate oropharyngeal *S. aureus* colonization in children.

2) Assess the safety, tolerability, and compliance of oropharyngeal decolonization among children and their caregivers. Using a structured instrument, we will survey trial participants and their parents/guardians on side effects, tolerability, and adherence of the 0.12% oral CHG rinse and placebo. Findings will serve as a counterpoint to any benefits derived from oral decolonization.

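### Aim 3 assigns the origin of breakthrough throat isolates against baseline isolates only, and plans no comparison of Day 28 throat with Day 7 nose

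*Combined protocol and SAP*

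**What the plan says.** All references are to the combined protocol and SAP.

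- **Hypothesis(es) and Aims, part A, secondary hypothesis b:** "recolonization of the oropharynx will come from isolates that colonize patients nose". No time point is attached to the nasal isolate.
- **Aim 3, opening text:** "We will compare breakthrough isolates with baseline nasal and oropharyngeal isolates to determine if breakthrough isolates represent either" one of three things: the child's original throat isolate, "recolonization with the baseline nasal isolate", or a newly acquired strain.
- **Aim 3, Data Analyses, hypothesis b:** in children cleared at Day 7, the Day 28 strain is expected to be either the nasal isolate present at baseline or a new "strain not present at baseline".
- **Aim 3, Data Analyses, hypothesis c:** nasal isolates at baseline and follow-up are compared with throat isolates from the same visit.
- **Aim 3, Data Analyses, sequencing list:** throat pairs are "15 between baseline and Day 7, and 18 between baseline and Day 28". About 30 nasal isolates are added, counted where they coincide with a throat isolate, for 96 in total.
- **Aim 3, Data Analyses, list of failure explanations:** the only nasal entry is "an isolate found at the nares at baseline".
- **Human Subjects:** "Consenting subjects will have their anterior nares and oropharynx swabbed at Visits 1, 2, and 3". The Follow-up visits section also has the nares swabbed at Visit 2 (Day 7).

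**The concern.** Recolonization is judged in children whose throat is negative at Day 7 and positive at Day 28. For them the Day 7 nasal isolate is the most recent nasal sample, taken when no throat isolate was found. It is the natural comparator for a hypothesis that the throat is reseeded from the nose. The swab is planned, but the isolate has no role in assigning origin and is not in the sequencing count.

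Two different histories then share one label. A strain the child picked up in the nose between baseline and Day 7, which later reached the throat, is classed as new. So is a strain that was never seen in the nose. What is at stake is how finely a descriptive aim can separate reseeding from the child's own nose from acquisition elsewhere.

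**Working it through.** **1. The plan's own count.** Inputs from Aim 3, Data Analyses: 30 children on CHG, 50% decolonized at Day 7, a 10% rise in colonization by Day 28, and about 45% nasal carriage among those colonized in the throat.

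- Throat-positive at Day 7: 30 × 0.50 = 15
- Throat-positive at Day 28: 15 + 0.10 × 30 = 18
- Pairs: 15 + 18 = 33; throat isolates: 2 × 33 = 66
- Nasal isolates: 0.45 × 66 = 29.7, about 30
- Total: 66 + 29.7 = 95.7, about 96, as stated

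By visit, the nasal isolates are 0.45 × 33 = 14.85 (baseline), 0.45 × 15 = 6.75 (Day 7) and 0.45 × 18 = 8.1 (Day 28). The 6.75 at Day 7 come from the 15 children who are throat-positive that day. A child cleared at Day 7 has no Day 7 throat isolate, so that child's Day 7 nasal isolate is outside the 96.

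**2. What the rule does with a Day 28 throat strain in a child cleared at Day 7.**

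| Where the strain was found earlier | Class under Aim 3 |
|---|---|
| Throat at baseline | Original throat isolate |
| Nose at baseline | Baseline nasal isolate |
| Neither site at baseline, nose at Day 7 | New |
| Neither site at baseline, not in nose at Day 7 | New |

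The last two rows are not separated. Hypothesis c cannot separate them, because these children have no Day 7 throat isolate and a match at Day 28 does not show which site was first.

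**3. How many children.** Let g be the number cleared at Day 7 and positive at Day 28, and c the number positive at Day 7 and negative at Day 28. Then 18 = 15 − c + g, so g = 3 + c. The minimum is g = 3 (the net figure). The maximum is g = 15, which needs every cleared child to recolonize and c = 12 of the 15 positives to clear.

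**4. Isolates the comparison would add.** The 45% describes people colonized in the throat; applying it to throat-negative children is an assumption.

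- g = 3: 3 × 0.45 = 1.35 (0.75 if 25% carry; 3 if all carry)
- g = 15: 15 × 0.45 = 6.75

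**5. Children whose class would gain information.** The documents give no rate of strain change. Assume that 10% to 40% of Day 7 nasal strains differ from the baseline nasal strain.

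- g = 3: 1.35 × 0.10 = 0.14 to 1.35 × 0.40 = 0.54
- g = 15: 6.75 × 0.10 = 0.68 to 6.75 × 0.40 = 2.7
- g = 3 with every child a nasal carrier: 3 × 0.10 = 0.3 to 3 × 0.40 = 1.2

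These are upper figures. The Day 28 throat strain must also match the Day 7 nasal strain, and that strain must not be the baseline throat strain. Both conditions lower the count.

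**The case against.** The strongest reply is that baseline is the right reference for the question Aim 3 asks. The abstract sets that question as pre-existing strain against newly acquired strain, and a strain in neither site at baseline is new to the child. This stands: the class is not wrong, only less informative than the swabs allow.

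It can also be said that follow-up nasal isolates are used. They are, in the same-visit comparison and in the search for *qac A/B* in the nares. Neither use reaches the children in question. The plan also intends to tell endogenous from exogenous sources at Days 7 and 28, but states no comparison that would do so for a strain gained between visits. The Limitations section discloses that not every isolate will be sequenced. The reason given is the cost of sampling other body sites, with nares and oropharynx kept.

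A reader might infer three stronger points, which the documents do not support:

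- **Bias against the Aim 3 hypothesis.** Aim 3's own hypothesis b accepts either a baseline nasal strain or a new one, so a result of new is among its predicted outcomes.
- **Consequences for the next regimen.** The structured abstract and the hypotheses section already include nasal decolonization in the follow-on trial, and the hypotheses section makes that trial depend on the primary hypothesis.
- **Acquisitions counted twice.** A strain first seen in the throat at Day 7 and still there at Day 28 is new relative to baseline in both pairs. The plan counts pairs, not acquisition events.

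**Conclusion.** The gap is real and narrow. Origin is assigned against baseline isolates only, no comparison of Day 28 throat with Day 7 nose is planned, and the sequencing list leaves out the nasal isolates it would need. The broad secondary hypothesis about the nose is therefore examined with less information than the planned swabs could give.

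The expected effect is under one child on the net figure of 3 recolonized children (0.14 to 0.54). This rests on 45% nasal carriage in throat-negative children and an assumed 10% to 40% strain change. Even the extreme of g = 15 gives at most 2.7 children before the two further matching conditions. Aim 3 is descriptive and unpowered, and the primary endpoint is unaffected. This is a cheap improvement, not a defect that threatens a conclusion.

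**What to change.** In Aim 3 (opening text and Data Analyses), before sequencing results are seen:

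- For each child throat-negative at Day 7 and throat-positive at Day 28, sequence the Day 7 nasal isolate if there is one and add it as a comparator for the Day 28 throat isolate.
- Report a match as present in the nose at Day 7, alongside whether the strain was present at baseline. This wording is preferable to nasal source, since a match gives the order of detection but does not prove the route.
- For children throat-positive at both follow-up visits, also compare the Day 28 throat isolate with the Day 7 one. Both are already on the list, so no extra sequencing is needed.

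The cost is a wording change and about 1 to 3 more isolates on the net figure, taking 96 to about 97 to 99, or about 7 more if all 15 cleared children recolonize. No new swabs are needed.
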